1. PREVIOUS STUDY HISTORY

Has this study ever been reviewed and rejected/disapproved by another IRB prior to submission to this IRB?

[No Yes – if yes, please explain:]

2. BRIEF SUMMARY OF RESEARCH

- *The summary should be written in language intelligible to a moderately educated, non-scientific layperson.*
- *It should contain a clear statement of the rationale and hypothesis of your study, a concise description of the methodology, with an emphasis on what will happen to the subjects, and a discussion of the results.*
- *This section should be ½ page*

We will be randomizing patients to either receive an adductor canal block in the operating room postoperatively as single shot of 20-30cc bupivacaine or to have a catheter inserted into the adductor canal which will be attached up to a continuous infusion pump of bupivacaine that will have a set flow rate over the next couple days. Our hypothesis is that patients will have better pain control, sleep, and decreased opioid consumption with the use of a continuous infusion pump

3. INTRODUCTION/BACKGROUND MATERIAL/PRELIMINARY STUDIES AND SIGNIFICANCE

- *Describe and provide the results of previous work by yourself or others, including animal studies, laboratory studies, pilot studies, pre-clinical and/or clinical studies involving the compound or device to be studied.*
- *Include information as to why you are conducting the study and how the study differs from what has been previously researched, including what the knowledge gaps are.*
- *Describe the importance of the knowledge expected to result*

ACL reconstruction is a common procedure performed ranging an estimated 60,000 to 175,000 times a year in the United states (6). Many factors can contribute to clinical outcome with ACL reconstruction, most notably with pain and rehabilitation. Numerous tactics are employed to help alleviate postoperative pain, ranging from simple conservative management such as ice and elevation, to oral and IV narcotics. Current trends in management aim to reduce the use of narcotics and to investigate various alternative modalities for achieving analgesia without compromising clinical outcomes. One way of achieving this is with use of peripheral nerve blocks. Administered by an anesthesiologist or certified nurse anesthetist, analgesia is delivered to a peripheral nerve using ultrasound guidance and in some incidences a catheter is then placed overlying the nerve sheath. This

catheter is then connected to a device with a reservoir that administers local anesthetic at a set rate that can be locked or manipulated by the user, which gives the theoretical advantage of continuous analgesia of the operative site.

Historically, other methods were used to combat post-operative pain. Buchko et al looked at intra-articular analgesia after arthroscopic ACL reconstruction and found an increased rate of chondrolysis, which was similar to other studies that looked at its use in the shoulder joint (11). Use of peripheral nerve blockade is not new practice and has been described throughout the literature. Manickam et al showed 100% success rate and full blockade after twenty minutes with use of the adductor canal block (12). The safety and efficacy of the Continuous Peripheral Nerve Block (CPNB) has been thoroughly investigated. Carvhalo et al found that the addition of a peripheral catheter added only 10 minutes to procedural time versus single shot peripheral nerve block (14). In a group of 35 trauma patients it was found that despite continuous peripheral nerve infusion, serum levels of Ropivacaine were well below toxic levels (15). A review article by Nicolotti et al found that the incidence of positive cultures of placed catheters varied widely from 6%-57%, but the actual incidence of positive cultures resulting in clinical infection was 0%-3.2% (13). The large discrepancy between the two values was found to be likely due to inadequate skin preparation and improper technique with removal.

Some studies have shown the efficacy of CPNB use and concluded with positive results. A multicenter prospective study of use of CPNBs found high quality postoperative pain reduction along with low rates of neurologic or infectious complications (1) and according to Enneking et al. CPNBs have been shown to improve patient satisfaction and improve rehabilitation compared to IV narcotics after orthopedic surgery for both upper and lower extremity (3). A more recent study prospectively looked at CPNB vs placebo (Normal Saline) performed in the upper extremity and found that there was a statistically significant reduction in pain, opioid use, sleep disturbances and increase in patient satisfaction scores (4). A large meta analysis by Richman et al looked at the efficacy of CPNBs and found statistically significant reduction in opioid use, pain up to 72 hours postoperative and decrease in episodes of nausea and vomiting (5) with use versus opioid analgesia.

In the lower extremity two main methods of block are employed, femoral nerve block (FNB) or adductor canal block (ACB). The use of FNB in ACL reconstruction, as shown by Mulroy et al, was found to have superior efficacy in pain control and reduction in opioid consumption when testing single shot FNB vs sham (9). One complication of FNB is quadricep muscle weakness, which Jaeger et al. demonstrated as a 49% reduction from baseline while ACB reduced strength 8% from baseline (10). Kwofie et al found that with ACB vs FNB that there was a statistically significant preservation in balance and strength in ACB compared to FNB (8). These studies show the advantages of ACB to anesthetize surgical sites without compromising quadriceps strength and balance. Abdallah et al showed that using ACB versus FNB reduced quadriceps weakness with similar functional outcomes and pain reduction in ACL reconstruction (7). The superiority of

continuous catheter delivery over single injection in regards to pain and reduction and opioid use have not been shown in the literature. To our knowledge there are no randomized controlled trials that compare single injection versus CPNB in the adductor canal following ACL reconstruction. In this study we look to compare these two methods of analgesia after ACL reconstruction examining the effects on pain control, opioid use, and satisfaction scores.

4. OBJECTIVE(S)/SPECIFIC AIMS AND HYPOTHESES

- *A concise statement of the goal(s) of the current study.*
- *The rationale for and specific objectives of the study.*
- *The goals and the hypothesis to be tested should be stated.*

OBJECTIVES	ENDPOINTS	JUSTIFICATION FOR ENDPOINTS
Primary		
To Compare the efficacy of two different modes of administration of peripheral nerve block for postoperative pain control after primary ACL reconstruction.	Pain control as measured by a visual analogue scale (0-10) on post operative day 1,2,3,4,7, and at first follow up visit (Day 14).	Our study seeks to better clarify the effectiveness of two postoperative pain control methods after ACL reconstruction. Visual analogue scale is commonly used to assess pain in postoperative patients. This is an easy way to assess patients pain in a quick and easy to understand method.
Secondary		
To compare the daily opioid consumption in patients post operatively after ACL Reconstruction.	This will be measured as daily consumption of oxycodone (morphine equivalents) on post operative day 1,2,3,4,7, and 14.	A secondary objective of our study would be to examine pain control objectively by opioid consumption each day. This is a secondary measure of the efficacy of pain control. The hope is that with better pain control via peripheral nerve block patients would be less reliant on opioid pain medication.
To determine the effectiveness of pain control and quality of sleep.	We will measure this by asking if they had a disturbance in their sleep or trouble getting to sleep through email surveys.	Our study wants to look at how pain control and sleep quality are correlated and to analyze if better pain control also allowed patients to have better postoperative sleep habits.

General Well Being	Short Form - 12 Survey given preoperatively and at 14 days post operatively.	This assessment test is to classify changes in general health and wellbeing, physical, and mental health.
Knee Assessment Score	International Knee Documentation Committee Subjective Knee Form (IKDC) to be given preoperatively and at 14 days post operatively.	Designed to assess patients with a variety of knee disorders.

5. RESOURCES AVAILABLE TO CONDUCT THE HUMAN RESEARCH

- *Explain the feasibility of meeting recruitment goals of this project and demonstrate a potential for recruiting the required number of suitable subjects within the agreed recruitment period*
 - *How many potential subjects do you have access to?*
- *Describe your process to ensure that all persons assisting with the trial are adequately informed about the protocol and their trial related duties and functions*

We will be recruiting patients from multiple surgeons who perform ACL reconstructions in an attempt to get a higher number of patients. Our recruitment is estimated to last 9-12 months to get an adequate number of patients. In the event that we are still in need we can extend the trial a few months in order to capture the adequate number of participants. All the involved providers and staff will be given the same instructions which are standardized to ensure that each facility and staff follow the same protocol. In addition, there will be a resident investigator or co investigator at each site to oversee the project.

6. RECRUITMENT METHODS

- *Describe the source of potential subjects*
- *Describe the methods that will be used to identify potential subjects*
- *Describe any materials that will be used to recruit subjects. A copy of any advertisements (flyers, radio scripts, etc.) should be submitted along with the protocol.*
- *If monetary compensation is to be offered, this should be indicated in the protocol*

We will include multiple different sites to increase our enrolment participants. All patients will be recruited in the outpatient setting after being diagnosed with an

ACL tear and deciding to have operative reconstruction with one of the participating surgeons. At that point, the patients will be recruited for the study. There will be no active recruiting outside of the surgeon's patient population that requires surgical reconstruction of their ACL.

In regards to retention, the patients will agree to the time points to participate in the email surveys from **REDCAP**. The surveys have automatic reminders every 2 hours in addition the study co-investigators will receive notifications and can contact the patient's if they do not complete the surveys at the agreed time. The patients will have a postoperative visit 10-14 days after the indicated surgery with the attending physician. The patient will also be contacted via telephone on post-operative day 1, 2, 3, 4 and 7 to assess for adverse events.

7. ELIGIBILITY CRITERIA

- *Describe the characteristics of the subject population, including their anticipated number, age, ranges, sex, ethnic background, and health status. Identify the criteria for inclusion or exclusion of any subpopulation.*
- *Explain the rationale for the involvement of special classes of subjects, such as fetuses, pregnant women, children, prisoners or other institutionalized individuals, or others who are likely to be vulnerable. You cannot include these populations in your research, unless you indicate such in the protocol*
- *Similarly, detail exclusionary criteria: age limits, special populations (minors, pregnant women, decisionally impaired), use of concomitant medications, subjects with other diseases, severity of illness, etc.*

INCLUSION CRITERIA - In order to be eligible to participate in this study, an individual must meet all of the following criteria:

1. Provision of signed and dated informed consent form
2. Stated willingness to comply with all study procedures and availability for the duration of the study
3. Male or female, aged >16 years old
4. In good general health as evidenced by medical history and deemed medically healthy enough to tolerate surgery by the patient's primary care physician
5. MRI with evidence of ACL tear, and wanting to have an ACL reconstruction surgery
6. Ability to take oral medication and be willing to adhere to the study intervention, including telephone calls and access to email.
7. Have a working telephone and electronic device with ability to access email that allows them for daily communication to complete the electronic correspondence.

EXCLUSION CRITERIA - An individual who meets any of the following criteria will be excluded from participation in this study:

1. Current daily opioid requirement exceeding the equivalent of 15mg morphine
2. Daily prescription of corticosteroid, tricyclic antidepressant, gabapentin, or tramadol
3. Carrying the diagnosis of chronic pain syndrome, uncontrolled anxiety, history of schizophrenia or related psychiatric disorders
4. History of alcohol or drug abuse/addiction
5. History of preexisting nerve damage in the surgical extremity
6. Knee surgery (same knee) in the previous 12 weeks
7. Anticipated knee surgery in the other knee planned in the ensuing 6 months
8. Diabetic patients with blood sugar values exceeding 250 mg/dl in the previous month
9. BMI >40Kg/m²
10. Pregnancy, which will be determined by a serum or urine HCG test on the day of surgery.
11. Incarceration
12. Inability to communicate with staff, including being unreachable by telephone and/or e-mail.
13. Revision ACL reconstruction
14. Patient reconsideration after initial agreement.
15. Non-English speaking subjects |

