post-operative care in the recovery suite with routine recovery room vital checks. For participants who are randomized to the continuous pump group, the pump will be assembled and filled by pharmacy and attached to the previously placed catheter while the participant is in the recovery room. Once the participants are awake and alert in the recovery room, a study investigator will review the study specifics again, including the surveys with written information on the questions that will be asked. They will also be given written instructions on how to use the continuous pumps and how to remove it. If the patient is uncomfortable removing it themselves, they can come to the office to have it removed. For participants who received a continuous pump the investigator will go over the function of the pump, troubleshooting, and how to remove the pump at home. All participants will be discharged home from the recovery room after they have met the routine discharge criteria following existing standard of care recovery room protocols. The patient will also be contacted via telephone on post-operative day 1, 2, 3, 4 and 7 to assess for adverse events.

- All data will be recorded in an encrypted database which is HIPPA and IRB compliant. All participant information will be labeled with a participant study identification number with no identifiable information documented.

Procedures	In Office visit/schedule	Study Day 1, Day of Operation	Study Day 2 (POD 1)	Study Day 3 (POD 2)	Study Day 4 (POD 3)	Study Day 5 (POD 4)	Study Day 8 (POD 7)	Final Study Day, in office visit (POD 10-14)
Informed consent	X							
Demographics	X							
Medical history	X							
Randomization	X							
Administer study intervention		X						
Physical exam (including height and weight)	X	X						X
Preoperative Workup per standard protocol	X							
Pregnancy test ^b		X						
Adverse event review and evaluation	X		X X X X X					
MRI/Imaging assessment	X							
Online RedCAP Surveys (VAS, sleep disturbance, Opioid Consumption)	X	X X X X X X X X						

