12. STATISTICAL ANALYSIS

- *Describe how your data will be used to test the hypotheses.*
- *State clearly what variables will be tested and what statistical tests will be used.*

- *Include sample size calculations.*
- *If this is a pilot study, state which variables will be examined for hypothesis generation in later studies.*

Blinding:

Due to the nature of the intervention (bolus block, continuous infusion pump), it is not possible to blind the physicians or patients.

Consent:

Consent will be obtained during the preoperative visit, prior to surgery.

Randomization:

Subjects will be randomly assigned in a 1:1 ratio to either bolus block or continuous catheter. The randomization will be stratified by hospital (Plainview, Franklin, Huntington, Long Island Jewish, or North Shore University Hospital).

The Biostatistics Unit will develop a randomization procedure using a permuted block design within the Biostatistics Randomization Management System (BRMS).

Additional details of the procedure, including required record keeping, will be further developed upon approval of this protocol. The Biostatistics Unit has extensive experience in implementing and in producing detailed documentation for such procedures.

Intention to Treat (ITT):

All analyses will be carried out according to the ITT principle. The ITT population will be all subjects randomized, regardless of what treatment they actually received. All patients will be analyzed in the group to which they were randomized.

Statistical Considerations:**Specific Aims:**

To compare the efficacy of two postoperative pain control methods (bolus block, continuous catheter) in patients undergoing ACL reconstruction.

Primary Outcome

Outcomes measured on post-operative days 0, 1,2,3,4,7, and at the post-operative follow-up visit. (Outcomes for days 0, 1,2,3,4, and 7 will be obtained via email and electronic surveys . Outcomes for the post-operative follow-up visit will be measured during the postoperative visit which takes place between days 10 and 14. This will be referred to as "Day 10").

- Pain Control

- Maximum pain will be measured on a scale of 0 to 10, where 0 represents no pain and 10 represents the worst possible pain. Patients will report the maximum pain felt in the 24 hours
- Current pain will be measured on a scale of 0 to 10, where 0 represents no pain and 10 represents the worst possible pain.
- Daily opioid consumption (expressed as morphine equivalents).

Secondary Outcomes

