Outcomes measured on post-operative days 1,2,3,4,7, and at the post-operative follow-up visit.

- Quality of Sleep
 - Trouble falling asleep due to pain (yes,no)
 - Wake due to pain (yes,no)

Outcomes measured at post-operative follow-up visit

- Satisfaction with surgery, on a scale of 0 to 10, where 0 represents extremely dissatisfied and 10 extremely satisfied
- Adverse events: Adverse events will be assessed at each visit. At the end of the study, each subject will be categorized as having had one or more adverse events, or not having had any adverse events.
- Serious Adverse events: Serious adverse events will be assessed at each visit and via telephone on post-operative day 1, 2, 3, 4 and 7. At the end of the study each subject will be categorized as having had one or more serious adverse events, or not having had any serious adverse events.

Statistical Methods:

Primary Outcomes:

For each outcome, repeated measures analysis of variance (RMANOVA), where post-operative pain control method (bolus block, continuous catheter) is the between subjects effect and post-operative day is the within subjects effect will be used to examine the association between pain control method and that outcome. Site (stratification variable) will be included as a covariate in each model. The interaction of post-operative control method and day will be included in the model. If the interaction is significant, then pairwise comparisons of pain control method at each day will be carried out within the RMANOVA model. If the usual assumptions required for the ANOVA model are not met, then a suitable transformation, or an appropriate non-parametric method will be used.

Secondary Outcomes:

For binary outcomes measured on days 1,2,3,4,7 and 10:

For each outcome, a generalized linear mixed model (GLMM) for binary clustered (i.e., hierarchical) data will be used to examine the association between pain control method and that outcome. GLMM will be used to account for the hierarchical structure of the data, (namely, multiple days within a subject). Site (stratification variable) will be included as a covariate in each model.

For binary outcomes measured on day 10 only:

For each outcome, logistic regression will be used to examine the association between pain control method and that outcome. Site (stratification variable) will be included as a covariate in each model.

For satisfaction with surgery:

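### Section 12 adjusts only for site and leaves out pre-operative opioid use and pain, which costs precision and leaves chance imbalance uncorrected

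*Combined protocol and SAP*

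**What the plan says.** **Entry.** Exclusion criterion 1 in Section 7 removes only patients with "Current daily opioid requirement exceeding the equivalent of 15mg morphine". Criteria 2 to 4 narrow the group further: "Daily prescription of corticosteroid, tricyclic antidepressant, gabapentin, or tramadol", "Carrying the diagnosis of chronic pain syndrome" and "History of alcohol or drug abuse/addiction" also exclude.

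**Opioid endpoint.** Section 12 lists, under Primary Outcome, "Daily opioid consumption (expressed as morphine equivalents"), a raw post-operative amount. The objectives table in Section 4 makes it secondary and words it differently: "This will be measured as daily consumption of oxycodone (morphine equivalents) on post operative day 1,2,3,4,7, and 14".

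**Pre-operative data.** In the Section 11 schedule, the row "Online RedCAP Surveys (VAS, sleep disturbance, Opioid Consumption") has a mark directly after its label, where the rows for consent and demographics have their office-visit mark. The efficacy paragraph of the same section sends surveys on post-operative days 1, 2, 3, 4, 7 and 14, and names only the SF-12 and IKDC as pre-operative.

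**Analysis.** Randomisation is 1:1 in permuted blocks, stratified by hospital. The repeated measures ANOVA for pain and opioid use contains method, day, their interaction and site: "Site (stratification variable) will be included as a covariate in each model". The outcome lists start at day 0 (pain, opioids) or day 1 (sleep). No baseline covariate, change score or opioid stratum appears.

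**The concern.** Patients can enter with different levels of opioid use and knee pain, and nothing in the design or the models accounts for those differences. On the Section 12 definition, a patient's habitual dose is part of the post-operative total. The variation it causes stays in the error term, and a chance excess of users in one arm of 39 moves the estimated opioid difference directly. The same holds for pre-operative pain. Day 0 cannot serve as a baseline, because it falls after randomisation and includes time after the block.

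The trial may already be collecting the values that would remove part of this variation. It is open-label, so an adjustment chosen after the data are seen would carry little weight. It has to be written down beforehand.

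**Working it through.** **1. The plan's own figure.** Inputs from Section 12: difference 2 points, SD 2.5, two-sided alpha 0.01, 80% power, single-day two-sample t-test. The noncentral t distribution gives 79.8% power at 38 per group and 81.0% at 39. The stated 39 per group is reproduced, as the smallest number that reaches 80%. It concerns pain only; no power is stated for the opioid endpoint.

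**2. Is there bias?** I simulated 40,000 trials per setting with no treatment effect and 39 per arm. Habitual users at 15 mg/day made up 5, 10, 20 or 30% of patients, and the SD from other sources was 10 or 20 mg (both assumed). With an unadjusted t-test, the mean arm difference was at most 0.04 mg and the type I error was 4.6 to 5.2% at nominal 5%. There is no bias and no inflation.

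**3. Chance imbalance in opioid use.** Let q be the share of patients at the full 15 mg/day. The documents do not give q, and putting every user at the ceiling is the upper case.

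- SD from habitual use = 15 × √(q(1−q))
- 95% range of the arm difference = ±1.96 × SD × √(2/39)

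| q | SD (mg) | 95% range (mg/day) |
|---|---|---|
| 5% | 3.27 | ±1.45 |
| 10% | 4.50 | ±2.00 |
| 20% | 6.00 | ±2.66 |

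**4. Opioid variance that adjustment could remove.** Share = 225q(1−q) / [225q(1−q) + S²], where S is the SD from all other sources (not in the documents; range assumed).

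| q | S = 10 mg | S = 20 mg | S = 30 mg |
|---|---|---|---|
| 5% | 9.7% | 2.6% | 1.2% |
| 10% | 16.8% | 4.8% | 2.2% |
| 20% | 26.5% | 8.3% | 3.8% |

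**5. Gain for pain.** Adjusting for a baseline with pre/post correlation r leaves a residual SD of 2.5 × √(1−r²). The documents give no r.

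| r | Residual SD | Power at 39 per group | n per group for 80% |
|---|---|---|---|
| 0 | 2.50 | 81.0% | 39 |
| 0.3 | 2.385 | 85.2% | 35 |
| 0.5 | 2.165 | 92.1% | 30 |

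These figures ignore the one degree of freedom spent on the covariate.

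**6. Which tests gain.** A baseline value is constant within a patient, so as a main effect it reduces between-patient error. That helps the overall method comparison and the single-day comparisons. It does little for the method-by-day interaction, which is tested within patients and which Section 12 makes the condition for the single-day comparisons.

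**The case against.** A reader might infer that habitual opioid use is counted as a treatment effect, so that the opioid result is contaminated. The documents do not support this. Allocation is randomised 1:1, prior use is balanced in expectation, and step 2 shows that the unadjusted test keeps its level. That test already allows for chance imbalance; what is lost is efficiency.

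A reader might also take the pre-operative survey as established. It is likely but not certain. The schedule row, as it reads in the text, has nine marks for eight columns, and the efficacy paragraph names no pre-operative pain or opioid survey.

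Four further objections stand in part:

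- The share of opioid users may be small, because criteria 2 to 4 already exclude several groups likely to use opioids regularly. On the oxycodone wording of Section 4, habitual use of another opioid would not be counted at all.
- The size of the opioid gain depends on an SD that the plan does not give. It is worthwhile near 10 mg and slight near 30 mg.
- A mandatory baseline covariate has a cost. Sections 11 and 23 allow consent on the day of surgery, so some patients may have no office-visit survey. Without a rule for missing values, the model could drop them from an analysis defined as all randomised subjects.
- The planned sample size is reproduced without any adjustment, so the trial is not invalid as written.

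None of these removes the case for prespecifying the covariate. They limit what can be claimed for it and add conditions to the fix.

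**Conclusion.** The point holds as one of precision and chance imbalance, not of bias. It should be acted on because the change is cheap and has to be made in advance.

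The stronger argument is pain: single-day power at 39 per group would rise from 81% to about 85 to 92% if r is 0.3 to 0.5. That margin is useful, since one patient fewer per arm already takes the plan below 80%. If r is near zero, almost nothing is gained and almost nothing lost.

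For opioids, chance differences of about 1.5 to 2.7 mg/day are possible if 5 to 20% of patients take the full 15 mg. The variance removed ranges from about 1% to 26% over the assumed values. The user share, the opioid SD and the correlation are all assumptions.

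**What to change.** 1. In Section 11, reconcile the efficacy paragraph with the schedule and state whether the pain, sleep and opioid survey is given pre-operatively.
2. Require it to be completed before randomisation, including for patients consented on the day of surgery. State when randomisation happens: the schedule marks the office visit, while the procedures text places it in the preoperative holding suite.
3. In Section 12, prespecify each outcome's own pre-operative value (maximum pain, current pain, opioid use in morphine equivalents, and the sleep items) as a covariate with site in the models already planned.
4. Add a missing-baseline rule that keeps every randomised patient in the analysis, for example mean imputation with a missing indicator.
5. Report baseline opioid use by arm.
6. Reconcile the opioid definitions in Sections 4 and 12, so that baseline and outcome count the same drugs.

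Eligibility and sample size do not change. The cost is a sentence or two per model, one degree of freedom for the covariate (a second where a missing indicator is used), and some care in collecting the survey on the day of surgery. If the survey turns out not to be planned, the items can be added to the pre-operative SF-12 and IKDC questionnaires.
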